6.1 INCLUSION CRITERIA

Participants are eligible to be included in the study only if all of the following criteria apply:

Age

I 01. Participant must be 14 to 69 years of age inclusive, at the time of signing the informed consent.

Type of participant and disease characteristics

I 02. Participants who present with uncomplicated *P. falciparum* malaria, with a fever as defined with axillary temperature ≥37.5 degree Celsius (°C) or oral/ rectal/ tympanic temperature ≥38°C or history of fever in the previous 24 hours (history of fever must be documented), with a mono-infection with *P. falciparum* and parasitemia (microscopically, blood smear) ≥3,000 and ≤50,000 asexual parasites/µL of blood.

Weight

I 03. Body weight within 35 and 90 kg (inclusive).

Sex

- I 04. Male and female
 - a) Male participants: A male participant must agree to use contraception as detailed in Appendix 5 of this protocol for 3 months after the last dose of study treatment and refrain from donating sperm during this period.
 - b) Female participants: A female participant is eligible to participate if she is not pregnant (see Appendix 5), not breastfeeding, and at least one of the following conditions applies:
 - Not a woman of childbearing potential (WOCBP) as defined in Appendix 5

OR

- A WOCBP who agrees to follow the contraceptive guidance in Appendix 5 for 3 months after the last dose of study treatment.

Informed Consent

I 05. Capable of giving signed informed consent (if the patient is ≥age defining majority) as described in Appendix 3, which includes compliance with the requirements and restrictions listed in the informed consent form (ICF) and in this protocol. Informed consent signed by the legally acceptable representative (LAR) of the minor patient (<18 years of age or <other age locally defining majority). In addition, in accordance with local regulation, minor participants with capacity for writing could sign off on an Assent Form. For those who are able to understand but with no capacity for writing the Assent Form would be read. In that case, an impartial witness could certify the document was read to the child.

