9.1.1.3 Definition of Parasite Clearance (by Microscopy)

A blood film will be considered 'negative' when the examination of 1000 white blood cells reveals no asexual parasites (see the study operational manual for more detail). Parasite clearance time is defined as the time of the first negative film, to be confirmed with a second negative film prepared within 6 to 12 hours of the first one. Parasite clearance will be concluded following confirmation of the second negative film.

If parasites have not cleared by 72 hours after IMP administration and criteria for rescue medication are not met at 72h, blood films should continue to be taken according to site standard practice (or at minimum every 8 hours) until parasite clearance is shown or until criteria for rescue medication are met (see Section 7.7.1).

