1.2.2 Secondary objectives

The secondary objectives of this study are:

- To evaluate the dose response of OZ439 combined with FQ on PCR-corrected and crude Day 28 ACPR
- To evaluate the dose-response of OZ439 combined with FQ on selected secondary endpoints
- To evaluate the safety and tolerability of different dosages of OZ439 in combination with FQ and FQ alone
- To characterize the PK of OZ439 in plasma, and of FQ and its active metabolite SSR97213 in blood

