2.1.4.2.9 Parasite Reduction Ratio (PRR)

Observed Parasite Reduction Ratio (PRR) will be provided at 24 h, 48 h, and 72 h.

The observed PRR_t (where t takes the following values 24h, 48h and 72h after IMP administration) is defined as the ratio of the number of parasites P_0 at time $t=0$ (before treatment) divided by the parasite count P_t at time t (post-treatment).

$$\text{PRR}_t = P_0/P_t$$

When calculating the observed parasite reduction ratio, if the post dose parasite count is equal to 0 (due to a negative parasitemia) then a value of 1 parasite/ μ L will be imputed to allow a parasite reduction ratio to be calculated.

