2.4.4.2.3 Observed Parasite reduction ratio

Descriptive statistics (such as arithmetic mean, geometric mean, standard deviation, median, Q1, Q3, minimum, and maximum) will be provided for each treatment arm.

Relationship between median blood concentrations for FQ (respectively blood concentrations for SSR97213 and plasma concentrations for OZ439) versus time-specific parasite reduction ratios (percent parasite reduction ratio [%PRR]) will be represented thanks to a scatter plot (one curve per treatment arm). Same analysis will be done for parasite clearance rate.

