High and increase from baseline	≥ 110 mmHg and increase from baseline ≥ 10 mmHg	Birth/0 to 27 days old : ≥ 50 mmHg and increase from baseline ≥ 10 mmHg 28 days/1 month to 23 months old: ≥ 54 mmHg and increase from baseline ≥ 10 mmHg 24 months/2 years to <6 years old: ≥ 59 mmHg and increase from baseline ≥ 10 mmHg 6 to <12 years old : ≥ 72 mmHg and increase from baseline ≥ 10 mmHg 12 to 16/18 years old : ≥ 78 mmHg and increase from baseline ≥ 10 mmHg
Heart rate supine (adults)		
Low and decrease from baseline	≤ 50 bpm and decrease from baseline ≥ 20 bpm	
High and increase from baseline	≥ 120 bpm and increase from baseline ≥ 20 bpm	

References:

- for adults: Criteria for Potentially Significant Abnormalities – for Phase 2/3 studies (oncology excepted) - Version 3.0 - 21-MAY-2014
- for children: Criteria for Potentially Clinically Significant Abnormalities for Studies in Children - Version 3.0 - 21-MAY-2014

Summary of statistical analyses

EFFICACY ANALYSIS

Endpoint	Analysis population	Primary analysis	Supportive analysis	Subgroup analysis	Other analyses
PCR-corrected ACPR at Day 28	PP	Logistic regression on exposure-response with odds ratio estimates, 2-sided 95% Wald CI and p-value	No	No	Proportion, percentage, 2-sided exact binomial 95% CI by treatment group
PCR crude ACPR at Day 28	PP	Logistic regression on exposure-response (resp. dose-response) with odds ratio estimates, 2-sided 95% Wald CI and p-value	No	No	Proportion, percentage, 2-sided exact binomial 95% CI by treatment group
PCR-corrected ACPR at Day 28	PP	Logistic regression on dose-response vs odds ratio estimates, 2-sided 95% Wald CI and p-value	No	No	Proportion, percentage, 2-sided exact binomial 95% CI by treatment group
Parasite Reduction Rate at 24, 48 h, and 72 h	PP	Descriptive statistics by treatment group and time of measurement.	No	No	No
Parasitemia data as a continuous endpoint	PP	Descriptive statistics by visit and treatment group. Time profile plots by treatment group	No	No	No
Parasite clearance rate	PP	Descriptive statistics by visit and treatment group.	No	No	No
Time to parasite Clearance, to fever clearance, 50% and 99% parasite reduction, recrudescence or re-infection, elapsed below LOQ of parasitemia.	PP	Kaplan Meier estimator and Cox model	No	No	No

SAFETY ANALYSES

Endpoint	Analysis population	Primary analysis	Supportive analysis	Subgroup analysis	Other analyses

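### Observed PRR: setting negative films to 1 parasite/µL puts a ceiling at the baseline count on PRR72, and no dose term or baseline adjustment is planned

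*SAP*

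**What the plan says.** SAP 2.1.4.2.9 defines the observed PRR at time t, which "is defined as the ratio of the number of parasites" before treatment divided by the count at t, for t = 24, 48 and 72 h. It then adds that "if the post dose parasite count is equal to 0 (due to a negative parasitemia) then a value of 1" parasite/µL is imputed. Protocol 9.1.1.3 calls a film negative when "the examination of 1000 white blood cells reveals no asexual parasites". Neither document converts that into a detection limit per µL. Entry parasitemia is "≥3,000 and ≤50,000 asexual parasites"/µL (Protocol 6.1).

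PRR is listed under the secondary objective "To evaluate the dose-response of OZ439 combined with FQ on selected secondary endpoints" (SAP 1.2.2; Protocol Table 1). For its analysis, SAP 2.4.4.2.3 says "Descriptive statistics (such as arithmetic mean, geometric mean, standard deviation, median, Q1, Q3, minimum, and maximum) will be provided for each treatment arm". It adds a display of drug concentrations against PRR that "will be represented thanks to a scatter plot (one curve per treatment arm"). The PRR row of the summary table closing SAP Appendix B reads "Descriptive statistics by treatment group and time of measurement", with no supportive or other analysis. Protocol Table 8 is likewise descriptive for PRR.

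**The concern.** Once a film is negative, the imputed denominator is fixed, so the patient's PRR holds nothing about the drug beyond the fact of clearance. What varies among cleared patients is the count they entered with. The better OZ439 works, the more patients sit at that ceiling, and the less the 72 h summaries can separate effective doses. A reader who sees similar PRR72 medians in the higher-dose arms could take a measurement ceiling for a dose plateau.

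The rule also rewards a high baseline: among cleared patients, a higher entry count gives a higher PRR. Protocol 5.4 treats baseline parasitemia as a strong covariate and expects efficacy to rise as it falls. The ACPR regressions (SAP 2.4.4.1.1 and 2.4.4.2.1.1) test log10 baseline as a covariate. The observed PRR analysis has neither that covariate nor a dose term.

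**Working it through.** The plan states no expected value, sample size or power for PRR, so there is no figure of its own to reproduce.

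**Identity.** PRR_t = P0/P_t. With P_t = 0 replaced by 1, PRR_t = P0/1 = P0. Cleared patients therefore run from 3,000 to 50,000 (log10 3.48 to 4.70), a spread of 50,000/3,000 = 16.7-fold.

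**Chance imbalance.** Appendix 8 of the protocol plans log10 baseline as Normal(4, 0.55), truncated. Cut to the eligible range, its SD is 0.323. For two arms of 30, SE = 0.323 × √(2/30) = 0.083, and 10^(1.96 × 0.083) ≈ 1.46. So 95% of chance imbalances in geometric-mean baseline lie within a 1.46-fold ratio. Randomization is stratified by site only (SAP 1.1).

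**How far PRR72 follows baseline.** The documents give neither clearance rates nor a detection limit. Assumed: log-linear decline, half-life CV 30%, 4 h lag, and a film negative below 8 or 1 parasite/µL and then set to 1. R² is for log10 PRR72 with log10 baseline, and with log clearance rate k.

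| Median half-life | Limit 8: negative | R² baseline / k | Limit 1: negative | R² baseline / k |
|---|---|---|---|---|
| 2.5 h | 100% | 0.99 / 0.00 | 99% | 0.97 / 0.00 |
| 3.5 h | 98% | 0.71 / 0.03 | 89% | 0.62 / 0.11 |
| 5 h | 80% | 0.09 / 0.45 | 52% | 0.08 / 0.66 |
| 7 h | 41% | 0.00 / 0.83 | 14% | 0.00 / 0.94 |
| 10 h | 8% | 0.00 / 0.90 | 1% | 0.00 / 0.97 |

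Baseline dominates only when roughly 90% or more of films are negative. That threshold is loose: at a limit of 8/µL these runs only bracket it between 80% and 98%.

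**Earlier time points.** At 24 h the R² with baseline is 0.00 throughout. At 48 h it is at most 0.04 for half-lives of 3.5 h or longer. It reaches 0.50 (limit 8, 95% negative) or 0.42 (limit 1, 81% negative) only at 2.5 h.

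**Compression between two arms of 30** (limit 8/µL, unadjusted t-test on log10 PRR72):
- 5 h vs 3.5 h: 80% and 98% negative; difference 0.25 log10, power 0.47. At 48 h the same pair gives 0.83 log10 and power 0.97.
- 3.5 h vs 2.5 h: 98% and 100% negative; difference 0.03 log10, power 0.07.
- 10 h vs 4 h: 8% and 94% negative; difference 1.81 log10, power 1.00.

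The PRR72 that would follow from the true clearance rate (k × 72/ln 10) differs by 1.93 log10 in the first pair and 2.57 in the second.

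**What each part of a fix gains.** Four arms of 30, half-lives 5/4.5/4/3.5 h, 3 h lag, limit 8/µL. Dose-trend power at 72 h is 53% with the SAP values unadjusted, 70% after adding log10 baseline, and 76% when negatives are also treated as censored. Reruns of this setting differ by a few points. At 48 h power is 99% either way.

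**The case against.** The strongest reply is that this is one descriptive secondary endpoint and the SAP has others without the ceiling. PRR24, PRR48 and PRR72 are also derived from the clearance rate (2.1.4.2.12). T_PC50 and T_PC99 get geometric means with 95% CIs by dose group (2.4.4.2.5), and time to clearance is analysed by Kaplan-Meier (2.4.4.2.6). Protocol Table 8 plans Cox models with dose and baseline parasitemia for the time-to-event endpoints, and the SAP summary table keeps Cox. This largely stands and limits the harm. It is not complete cover: 2.4.4.2.4 drops patients whose linear fit has R² below 0.75, and observed PRR is itself named in the protocol.

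The value 1 is not arbitrary either, since SAP 2.1.4 counts a film as positive from 1 parasite/µL. The 8/µL limit used above is an assumption (one parasite per 1000 white cells at 8000 white cells/µL).

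Several stronger readings are tempting and not supported:
- A reader might infer that PRR72 mostly reports baseline. That needs the negative share at 72 h, which the documents do not give. At about 80% negative it is false, and arms that differ in the share negative still separate.
- One might extend the problem to all three times. PRR24 is untouched, and PRR48 needs very fast clearance.
- One might call it bias. Arms are randomized, so baseline adds noise and a ceiling, not a systematic difference.
- One might cite the true 72 h contrast as lost information. For 5 h vs 3.5 h, simulated true median reductions are 14,159 and 852,063, about 60-fold, against PRR72 medians of 7,811 and 10,698. But from 10,000/µL the larger reduction means 10,000/852,063 ≈ 0.01 parasite/µL, which no film can show.
- One might say planned power is lost. No test of PRR is planned.

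**Conclusion.** The point holds in limited form. It is certain from the text that a cleared patient's observed PRR equals the baseline count, and that the PRR analysis has no dose term or baseline adjustment despite its dose-response objective. How much PRR72 suffers is conditional: under the assumed half-lives, lag, CV and detection limits, compression is material at about 80% negative, and baseline becomes the main source of variation at roughly 90% or more. Most of the recoverable precision at 72 h comes from baseline adjustment (17 of the 23 points, 53% to 70%), with censoring adding 6. The consequence is a 72 h table that could be misread as a dose plateau. The primary analysis is not touched.

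**What to change.** 1. In SAP 2.1.4.2.9, state the detection limit L per µL and treat a negative film as right-censored: log10 PRR greater than log10(P0/L). With L = 8, for example, the bounds run from 3,000/8 = 375 to 50,000/8 = 6,250.
2. In 2.4.4.2.3 and the PRR row of the summary table, add a censored regression of log10 observed PRR at each time point on OZ439 dose with log10 baseline parasitemia as covariate, reporting the slope and 95% CI. The Tobit model in 2.1.4.2.10 is a precedent only: it is optional there and estimates the clearance rate.
3. Report the percentage of negative films by arm and time beside the PRR summaries. The existing descriptive table can stay.
4. While editing that row, reconcile its population: the table says PP, whereas 2.4.4.2 puts this endpoint on the mITT population only.

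The cost is SAP wording and one small model per time point, from data already collected. The downside is that a PRR72 median may have to be reported as greater than some value when most films are negative.
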